STUDY00009531 – formative secondary data analysis in 9531 led to development of computational models that will be used in this application

1.4 Externally-imposed urgency or time deadlines. Are there any externally-imposed deadlines or urgency that affect the proposed activity?

HSD recognizes that everyone would like their IRB applications to be reviewed as quickly as possible. To ensure fairness, it is HSD policy to review applications in the order in which they are received. However, HSD will assign a higher priority to research with externally-imposed urgency that is beyond the control of the researcher. Researchers are encouraged to communicate as soon as possible with their HSD staff contact person when there is an urgent situation (in other words, before submitting the IRB application). Examples: a researcher plans to test an experimental vaccine that has just been developed for a newly emerging epidemic; a researcher has an unexpected opportunity to collect data from students when the end of the school year is only four weeks away.

HSD may ask for documentation of the externally-imposed urgency. A higher priority should not be requested to compensate for a researcher's failure to prepare an IRB application in a timely manner. Note that IRB review requires a certain minimum amount of time; without sufficient time, the IRB may not be able to review and approve an application by a deadline.

	No
	Yes

→ If yes, briefly describe the urgency or deadline as well as the reason for it.

1.5 Objectives Using lay language, describe the purpose, specific aims, or objectives that will be met by this specific project. If hypotheses are being tested, describe them. You will be asked to describe the specific procedures in a later section.

If this application involves the use of a HUD “humanitarian” device: describe whether the use is for “on-label” clinical patient care, “off-label” clinical patient care, and/or research (collecting safety and/or effectiveness data).

Our overarching aim is to implement a natural language processing (NLP) model into the previously developed Mobile WACH SMS platform and test its acceptability and impact on healthcare workers response time.

Aim 1: Validate performance of an NLP model trained to detect urgent client SMS.

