Ten nurses from Mobile WACH studies will be presented with client messages from previous Mobile WACH studies, annotated with urgency predictions from the top 3 best performing NLP models. Each nurse will be asked to report their agreement with each prediction. The model with the highest sensitivity and specificity compared with the nurse “gold standard” determination will be selected for implementation in the Mobile WACH system.

Aim 2: Using a human-centered design approach, adapt the Mobile WACH system nurse interface to dynamically display urgent incoming messages.

Interactive focus groups will be conducted with 6-10 nurses from Mobile WACH studies and MOH facilities to collectively design a user interface that integrates real-time urgency classification of incoming messages and highlights messages classified as urgent.

Aim 3: Pilot the adapted Mobile WACH interface (AI-NEO) that identifies urgent client SMS and evaluate its acceptability and effect on nurse response time.

We will enroll 80 pregnant women to receive the AI-NEO SMS intervention. Women will be enrolled at 28-36 weeks gestation and will receive automated SMS regarding neonatal health from enrollment until 6 weeks postpartum, and will have the ability to interactively message with study nurses. Participant messages will be automatically categorized by urgency. We will evaluate intervention acceptability and recommended improvements among clients and nurses using quantitative and qualitative data collection at study exit (quantitative questionnaires with all client participants and qualitative interviews with 4 nurses). We will compare nurse response time to urgent and non-urgent participant messages with the ongoing Mobile WACH NEO trial, in which a non-adapted Mobile WACH system is used.

1.6 Study design. Provide a one-sentence description of the general study design and/or type of methodology.

Your answer will help HSD in assigning applications to reviewers and in managing workload. Examples: a longitudinal observational study; a double-blind, placebo-controlled randomized study; ethnographic interviews; web scraping from a convenience sample of blogs; medical record review; coordinating center for a multi-site study.

Mixed methods design phase followed by pilot longitudinal cohort study.

1.7 Intent. Check all the descriptors that apply to your activity. You must place an “X” in at least one box.

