b. Experience and preliminary work. Briefly describe experience or preliminary work or data (if any) that you, your team, or your collaborators/co-investigators have that supports the feasibility and/or safety of this study.

It is not necessary to summarize all discussion that has led to the development of the study protocol. The IRB is interested only in short summaries about experiences or preliminary work that suggest the study is feasible and that risks are reasonable relative to the benefits. Examples: Your team has already conducted a Phase 1 study of an experimental drug which supports the Phase 2 study being proposed in this application; your team has already done a small pilot study showing that the reading skills intervention described in this application is feasible in an after-school program with classroom aides; your team has experience with the type of surgery that is required to implant the study device; the study coordinator is experienced in working with subjects who have significant cognitive impairment.

We have developed NLP models with promising performance for detection of urgent client messages.

Using 1497 messages sent by the 30 most active participants in the Mobile WACH NEO pilot study, we developed NLP models using message metadata, word frequencies and contextual word embeddings to detect clinical urgency of messages. **Fig. 3** displays precision-recall curves summarizing performance of 6 representative models using a variety of linguistic features and modeling approaches. To evaluate potential clinical usefulness of models, we identified two potential model applications and associated evaluation criteria. A “triage” model rules out messages by identifying with very high recall (sensitivity) the messages of interest (i.e. urgent messages) for healthcare workers to focus their review on, while significantly reducing the number of messages reviewed. A “prioritize” model identifies messages of interest with very high precision (positive predictive value), allowing healthcare workers to read those messages first, while still reading the remaining messages later. Each ideal model occupies a region on the precision-recall plot; a model whose precision-recall curve falls in one of the two regions would be a candidate model for pilot testing. To date, we have developed one model close to the “triage” region. We are continuing to optimize model performance and are optimistic we can achieve further performance gains.

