5 PROCEDURES

- 5.1 Study procedures.** Using lay language, provide a complete description of the study procedures, including the sequence, intervention or manipulation (if any), drug dosing information (if any), blood volumes and frequency of draws (if any), use of records, time required, and setting/location. If it is available: Upload a study flow sheet or table to **Zipline**.

For studies comparing standards of care: It is important to accurately identify the research procedures. See UW IRB [POLICY Risks of Harm from Standard Care](#) and the draft guidance from the federal Office of Human Research Protections, [“Guidance on Disclosing Reasonably Foreseeable Risks in Research Evaluating Standards of Care”](#); October 20, 2014. Information about pediatric blood volume and frequency of draws that would qualify for expedited review can be found in this [reference table](#) on the Seattle Children’s IRB website.

Aim 1 – model validation

Nurses will self-administer an electronic tablet-based questionnaire that will present them with a series of participant messages and ask them to categorize each message’s urgency according to a provided definition. The questionnaire will also include open-ended questions to enter comments on each assessment. No identifiable information will be collected.

Aim 2 – interface design

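### Aim 1 uses one nurse-labelled set to choose among three models and to validate the choice; reported as validation, the winner's accuracy would be biased upward

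*Protocol*

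**What the plan says.** Protocol section 1.5 (Objectives) gives the purpose of Aim 1 as "Validate performance of an NLP model trained to detect urgent client SMS".

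The same section then describes one exercise. Ten nurses "will be presented with client messages from previous Mobile WACH studies", "annotated with urgency predictions from the top 3 best performing NLP models". The rule for what follows is: "The model with the highest sensitivity and specificity compared with the nurse" reference label "will be selected for implementation in the Mobile WACH system".

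Section 5.1 (Study procedures, Aim 1) also describes one exercise only, a tablet questionnaire that will "present them with a series of participant messages and ask them to categorize each message’s urgency according to a provided definition".

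Neither section gives the number of messages, the proportion expected to be urgent, or a second labelled set. Aim 3 evaluates acceptability and nurse response time. It describes no new labelling from which sensitivity or specificity could be estimated again.

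**The concern.** The same labels do two jobs. They rank three models, and they are the only labels in the protocol against which the top-ranked model can be validated. The highest of three noisy estimates exceeds that model's true value on average, because the winner is partly the model that was lucky on these particular messages.

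What is at stake is how the Aim 1 result is read. Section 1.8b describes a triage use in which very high sensitivity is needed so that nurses can concentrate their review. If urgent messages are the smaller class, sensitivity is the more inflated measure, and an inflated sensitivity understates how many urgent messages the model misses.

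**Working it through.** **Plan's own figure.** There is none to reproduce. The protocol states no message count, urgency prevalence, target accuracy or accuracy for the winner.

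**Inputs from the protocol.** Three candidate models; one labelled set; choice by sensitivity and specificity together (section 1.5).

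**Assumed inputs.**
- True specificity 0.80 for all three models; true sensitivity either 0.80 for all, or 0.75, 0.80 and 0.85.
- Choice by the sum of sensitivity and specificity. The protocol gives no rule for when the two disagree.
- 30, 100 or 200 urgent messages, with *k* = 4 to 9 non-urgent messages per urgent one.
- Errors of the three models on the same message correlated through a latent normal variable, correlation 0.3 to 0.7.

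**Hand check for three equal models with uncorrelated errors.** The expected maximum of three independent standard normal values is 0.846. With *n* urgent messages, the variance of sensitivity is Vs = 0.16/*n* and that of specificity is Vp = 0.16/(*kn*). Choosing on the sum gives

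sensitivity optimism ≈ 0.846 × Vs/√(Vs + Vp) = 0.846 × √(0.16/*n*) × √(*k*/(*k*+1)).

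- *n* = 30, standard error 7.30 points: 0.846 × 7.30 × 0.894 = 5.5 points (*k* = 4); 0.846 × 7.30 × 0.949 = 5.9 (*k* = 9).
- *n* = 100, standard error 4.00: 3.0 and 3.2 points.
- *n* = 200, standard error 2.83: 2.1 and 2.3 points.

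Positive correlation between the models' errors lowers these values. Specificity optimism is Vp/Vs = 1/*k* times the sensitivity optimism: roughly a quarter at *k* = 4, a ninth at *k* = 9, and equal to it in balanced classes.

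**Simulation with correlated errors.** Optimism is the winner's observed minus true sensitivity, averaged over repeated sets.

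| Urgent messages | Three equal models (0.80) | Models differ (0.75/0.80/0.85) |
|---|---|---|
| 30 | about 4 to 5 points | about 3 to 4 points |
| 100 | about 2 to 3 points | about 0.7 to 1.4 points |
| 200 | about 1.5 to 2 points | about 0.4 to 0.6 points |

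Specificity optimism in these settings is about 1 point or less (at most about 1.2, with 30 urgent messages and *k* = 4). With balanced classes and 30 urgent messages the two measures share the bias: 3.1 to 3.9 points for sensitivity and 3.2 to 4.1 for specificity.

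**Other starting values.** With three equal models at 0.85/0.85 and latent correlation 0 to 0.8, sensitivity optimism is 4.4 to 6.3 points with 20 urgent messages, 1.7 to 2.7 with 100 and 1.1 to 1.6 with 299. With true sensitivities of 0.80, 0.85 and 0.90 it is 2.9 to 5.0, 0.4 to 1.2 and 0.1 to 0.3 points. The bias is upward in every scenario and below one standard error of the sensitivity estimate.

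**The case against.** The strongest reply has four parts.

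1. **No accuracy for the winner is printed, and none is promised from this set.** This stands. A reader might infer that a stated accuracy is wrong. The documents contain no such figure, so the point is conditional on the selection-set estimate being reported as the validation.

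2. **Hold-out sets and optimism corrections belong in an analysis plan, which is not shown.** This stands in part. Such a plan could add a correction, and one questionnaire does not rule out reserving some messages. But it is the protocol itself that calls the exercise a validation and makes it the means of choosing the model.

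3. **The bias changes no decision.** This stands. Aim 1 sets no accuracy threshold, and the top-ranked model is implemented whatever its value. A reader might infer that an inflated figure is what justifies deployment, or that live performance in Aim 3 will look like a deterioration. Neither is supported: deployment follows from rank alone, and Aim 3 plans no accuracy estimate to compare with.

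4. **The size is not a bound.** This stands. Exact equality of the three models is the unfavourable case. The optimism is close to nil when one model is clearly better and the set is large. That urgent messages are the smaller class is also an assumption.

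**Conclusion.** The point holds in conditional form. As described, one labelled set serves both to select and to validate, so the winner's sensitivity and specificity on that set are biased upward if reported as validated performance. The selection itself is sound.

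Under the assumptions above, the sensitivity optimism runs from about half a point (200 urgent messages, models that differ) to about 5 points (30 urgent messages, equal models). Specificity is affected by about 1 point or less unless the classes are balanced. The direction follows from the design; the size cannot be fixed from the protocol. This is a minor point with a cheap remedy. It says nothing about Aim 3.

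**What to change.** Do one of the following.

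- **Split.** Set aside a random part of the messages, divided by client, choose the model on the rest, and report its sensitivity and specificity from the part set aside. This removes the selection bias but widens the interval. With sensitivity 0.80, 100 urgent messages and independent messages, the 95% half-width is 1.96 × √(0.16/100) = 7.8 points; on half of them it is 1.96 × √(0.16/50) = 11.1 points.
- **Bootstrap.** Resample clients, choose the model again in every resample, and subtract the estimated optimism. All messages are kept, at the price of a little more analysis. In a trial run this removed about two thirds of the bias, not all of it. It needs each message linked to its client, and the ten nurses' answers first combined into one reference label.
- **Rename.** If neither is wanted, describe Aim 1 as model selection, and state beside any accuracy given for the chosen model that the same labels were used to choose it.

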capability to respond and spontaneously message a nurse based at the clinic. During pregnancy, automated SMS will be delivered weekly. Two weeks prior to the participant’s estimated due date (EDD), daily messaging will begin, and will continue for two weeks after delivery is ascertained. If delivery is not confirmed by 43 weeks gestational age, the participant will be automatically moved to the postpartum messaging track. Thereafter, SMS will be delivered every other day for the remaining four weeks. Automated SMS will be delivered at times and in languages based on patient preferences. We have partnered with a local premium rate service provider (PRSP), Africa’s Talking, to provide SMS dialogue free of charge to participants. Women who experience pregnancy or infant loss will be enrolled into an infant loss track where they will receive messages of support. All AI-NEO pilot participants will receive the intervention.

Data collection: Participants will be followed from enrolment (28-36 weeks gestation) up to 18 weeks postpartum. All clinical care will be managed through the existing MCH infrastructure. The study visit schedule will be aligned to routine postpartum and infant visits: enrolment visit in pregnancy (28-36 weeks gestation), 2 weeks postpartum and 6 weeks postpartum. Active tracing will be performed through phone calls and home visits to maximize completeness of data at study visits. Participants who do not report their delivery by 40 weeks will be contacted by phone, followed by home tracing if not reached by phone. Further, participants who are 1 week late for their 2-week or 6-week postpartum visits will be traced by phone. Participants who are 2 weeks late for their 6-week visit and cannot be reached by phone will be traced at their home. Participants who do not wish to come to clinic for their 2-week or 6-week visit will be offered to complete their visits by phone or at home in locations that ensure participant safety and confidentiality. This approach has been successful and acceptable in our previous studies in this population. During the consent process, study staff will collect contact information and permission to contact a family member or trusted individual who they may contact in case of long-term lack of communication from the participant. This person may be contacted as part of active tracing.

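### Aim 3 calls a non-randomised contrast with the NEO trial an effect on nurse response time, and states no urgency label for the NEO messages

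*Protocol*

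**What the plan says.** The overarching aim in section 1.5 is to put the language model into the platform and "test its acceptability and impact on healthcare workers response time". Aim 3 is to "evaluate its acceptability and effect on nurse response time". The comparison itself is one sentence: "We will compare nurse response time to urgent and non-urgent participant messages with the ongoing Mobile WACH NEO trial", followed by the clause "in which a non-adapted Mobile WACH system is used". Section 1.8b repeats the plan as a comparison of workflow in the NEO RCT with workflow in the NLP-enabled variant.

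On allocation, section 1.6 calls the design a pilot longitudinal cohort, and section 5.1 states: "All AI-NEO pilot participants will receive the intervention".

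On urgency, Aim 3 says of the pilot: "Participant messages will be automatically categorized by urgency". Two other places describe labelled messages. In Aim 1, nurses judge "client messages from previous Mobile WACH studies". The model development in section 1.8b was done "Using 1497 messages sent by the 30 most active participants in the Mobile WACH NEO pilot study".

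Section 1.3 says Aim 3 will be nested within study 6395, which section 5.1 identifies as the NEO RCT. The term is not explained further.

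**The concern.** Response time depends on who staffs the queue, how full it is and which messages are counted. The protocol fixes none of these equally for the two sides. Without randomisation between the adapted and the non-adapted interface, a difference in facility, nurse, workload or calendar period can pass for a difference due to the display.

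The split by urgency adds a second problem. If urgent means flagged by the model in AI-NEO and something else in NEO, the two urgent groups are different kinds of message, and so are the two non-urgent groups. A difference between them could then arise with no change in how fast nurses work. The stake is the main quantitative conclusion of the pilot, since section 1.8b gives this empirical comparison as the reason for running it.

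**Working it through.** The protocol gives no response-time figure to reproduce. The check sets the statements side by side and then illustrates the labelling problem.

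**Side by side**

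- *Platform.* AI-NEO is a single group of 80 women, all on the adapted system (sections 1.5 and 5.1). NEO uses the non-adapted system. Platform therefore coincides with study.
- *Comparator.* Sections 1.5 and 1.8b name the NEO trial. Section 1.8b places it in Nairobi and Western Kenya. Neither section limits the comparator to particular facilities, nurses or dates, and neither maps AI-NEO to one of the two regions.
- *Urgency label in AI-NEO.* Automatic, from the selected model.
- *Urgency label in NEO.* None stated. Aim 1 uses previous studies, and on a plain reading the ongoing RCT is not one of them. The 1,497 development messages come from the NEO pilot, a separate row of Table 1. The stratified comparison is thus defined on one side only.
- *Size of the NEO side.* Table 1 gives 2,500 clients and NA for every message count, so bias cannot be computed from the documents.

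**Illustration of unequal labels (all inputs assumed)**

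Suppose the interface has no effect. In both studies nurses answer truly urgent messages in 2 h on average and all others in 6 h. If a share PPV of the messages labelled urgent are truly urgent, then

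mean time of messages labelled urgent = PPV × 2 + (1 − PPV) × 6.

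| PPV of label | Calculation | Mean (h) | Minus 2.0 h under a perfect label |
|---|---|---|---|
| 0.30 | 0.6 + 4.2 | 4.8 | 2.8 |
| 0.50 | 1.0 + 3.0 | 4.0 | 2.0 |
| 0.80 | 1.6 + 1.2 | 2.8 | 0.8 |
| 0.95 | 1.9 + 0.3 | 2.2 | 0.2 |

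If NEO messages were labelled perfectly by nurses and AI-NEO messages by a model with PPV 0.50, the display would appear to slow responses by 4.0 − 2.0 = 2.0 h. If the NEO label had PPV 0.50 and the AI-NEO label 0.95, it would appear to speed them up by 4.0 − 2.2 = 1.8 h. With the same PPV on both sides the difference is 0. The artefact can go either way.

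The lower PPV values cannot be excluded. Section 1.8b says that the best model so far lies close to the triage region, which is defined by high recall rather than high precision, and that optimisation continues.

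**The case against.** The strongest reply is that this is a pilot described in lay language on an ethics form. It openly calls itself a cohort study and nowhere claims randomisation. The facilities, dates and labelling rule of the comparison set may also be in a statistical analysis plan that is not shown. Part of this stands: the absence of a model, an adjustment set or a power calculation is no fault here. But the causal aim, the external comparator and the split by urgency are fixed in this document, and lay wording does not make a non-randomised contrast an effect.

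Several stronger readings are tempting and are not supported:

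- *That the comparator is the entire NEO RCT.* The text names the trial without restriction. It does not say that everything will be used.
- *That follow-up windows differ by a calculable amount.* Table 1 gives NEO follow-up to 2 months, against messaging to 6 weeks in AI-NEO. The entry is coarse and may be a rounding, and any percentage would need assumed enrolment and delivery times.
- *That section 5.5 shows NEO messages will not be available.* Its short list also omits AI-NEO's own messages. The form does not ask for information from section 5.1 to be repeated, and section 9.6 lists platform messages as study data.
- *That nesting contradicts the exclusion in section 2.2 of women in another study.* Nesting of platform or site is compatible with that exclusion. The term is undefined, not contradictory.
- *That the comparison must be limited to the same dates.* If the same nurses answer both queues, highlighting urgent AI-NEO messages could delay NEO messages or free time for them. Concurrent NEO messages would then be the ones most exposed to this spillover.

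**Conclusion.** The concern holds in this form: the protocol announces an effect or impact on response time from a non-randomised contrast, leaves the comparator unrestricted, and splits the contrast by an urgency label that it states for one side only. Taken literally, differences in site, nurse load, period or labelling would be credited to the interface.

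The direction and size of any bias are unknown. It may be small if sites and workload are similar and the labels are in fact made alike. The hours in the table rest on assumed response times and PPVs. They show only that unequal labels are enough to create or hide a difference. The point is worth correcting before the comparison is made. It does not call the pilot itself, or its acceptability objective, into question.

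**What to change.** In section 1.5 (Aim 3) and section 5.1:

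1. Run the same final classifier retrospectively on the NEO RCT messages, so that urgent and non-urgent are defined identically in both sets.
2. Take the NEO comparator from the AI-NEO facilities and from the same window, enrolment to 6 weeks postpartum, as far as possible, and state what is not possible. If the same nurses answer both queues, also show NEO messages from those facilities before AI-NEO launch, because concurrent ones may be affected by spillover.
3. Report client messages per nurse per day in each set.
4. Describe the result as a non-randomised, exploratory comparison, not as an effect or impact.

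The work is protocol wording, one classifier run and a filter on time stamps that the platform already stores (section 1.8a). The price is fewer NEO messages and a wider interval, by an amount that the documents do not determine. Restriction is possible only as far as sites overlap. Pre-launch NEO messages avoid spillover but bring back a difference in calendar time, so they should be shown beside the concurrent ones and not replace them. A common classifier makes the definition equal, but it does not remove differences between nurses or in the mix of messages. The exploratory wording is therefore needed even after the other changes.
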